#### Bacteriostatic Saline as a Local Anesthetic in Minor Eyelid Procedures

#### Introduction

Benzoyl alcohol is an aromatic alcohol that has been used in healthcare primarily as an antibacterial preservative agent in bacteriostatic saline. It has also been shown to have anesthetic properties, and has been demonstrated to cause less pain with infusion compared to lidocaine1, while maintaining adequate pain relief for certain procedures such as IV insertion2,3, cervical anesthesia4 and hip injections5. It has also been demonstrated to provide pain relief when used to reconstitute botulinum toxin and to have greater cost effectiveness compared to lidocaine10,6.

The use of bacteriostatic saline alone as an anesthetic for incisional procedures in the periocular area has not yet been studied.7 In a prospective, randomized, double-blinded randomized control trial comparing lidocaine buffered with either bacteriostatic saline or sodium bicarbonate in incisional eyelid surgery, lidocaine buffered with bacteriostatic saline showed greater comfort on injection with bacteriostatic saline buffer while providing a similar level of anesthesia,8 bacteriostatic saline with epinephrine was significantly less painful on infiltration. In a dermatologic randomized controlled trial, compared to lidocaine buffered with sodium bicarbonate for superficial procedures such as shave excision, scissor excision, superficial curettage but not deep punch biopsy or flap closures.9

### **Clinical question**

Does bacteriostatic saline an adequate level of anesthesia compared to lidocaine with epinephrine while reducing pain associated with medication infusion in minor eyelid procedures.

### **Participants**

Patients >= 18 years old undergoing clinic-based "minor" eyelid procedures in clinic with at least one lesion.

Inclusion criteria:

- 1. Age >=18 years old
- 2. Any eyelid lesion presenting to clinic setting Exclusion criteria
- 1. Any other topical, PO or IV sedating medications given alongside procedure
- 2. Allergy to lidocaine or epinephrine

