#### Intervention

- 1. 0.9% Bacteriostatic Saline
- 2. 2% Lidocaine + 1/100,000 Epinephrine

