# **Study Protocol**

Prior to clinic day, patient list will be reviewed to identify potentially eligible patients. On the procedure day, eligible patients will be approached for participation following initial evaluation by attending physician. If patient amenable, patient will be consented for study. Photograph will be taken of the lesion directly in electronic medical record, and lesion circled using annotate function. Each lesion will be randomized separately using iPhone-based randomization application to either bacteriostatic saline or lidocaine with epinephrine. Fellow will be unblinded, attending physician blinded. Medication will be drawn up by fellow and handed to attending physician who will inject the medication. Immediately following injection, patient will be asked pain level on 0 to 10 scale, which was noted. Five minutes will be allowed to pass and then procedure will be commenced. If patient has more pain than acceptable to them, additional study agent will be injected and procedure re-started. If continued presence of pain, one more additional trial of the study agent will be allowed. If patient continues to have pain, medication will be defaulted to standard of care (lidocaine with epinephrine). Alternatively, if patient requests standard of care at any point, medication will be switched to this. Immediately following procedure, patient will be asked pain level on 0 to 10 scale, which was noted. Number of reinjections or need to default to standard of care will be noted. Bleeding level (Mild, moderate, or severe) will be noted. Mild is defined as not needing pressure to stop. Moderate is defined as needing five minutes or pressure to stop. Severe is defined as needing cautery or a pressure patch. Immediately following injection, patient will be asked pain level on 0 to 10 scale.

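### The only allergy exclusion covers the lidocaine arm, so a patient with a known allergy to the preservative alcohol in bacteriostatic saline is eligible as written and can be randomised to it

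*Combined protocol and SAP*

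**What the plan says.** Participants lists two inclusion and two exclusion criteria. The inclusions are adult age and "Any eyelid lesion presenting to clinic setting". The exclusions are the use of other sedating medication with the procedure and "Allergy to lidocaine or epinephrine". No other section has any wording on allergy, hypersensitivity or contraindications.

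Intervention lists two agents: "0.9% Bacteriostatic Saline" and lidocaine with epinephrine. The Introduction explains why the first might work as an anesthetic. It describes an aromatic alcohol used "primarily as an antibacterial preservative agent in bacteriostatic saline" and adds: "It has also been shown to have anesthetic properties".

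On allocation and delivery, Study Protocol says "Each lesion will be randomized separately using iPhone-based randomization application", to one agent or the other. Before that, "eligible patients will be approached for participation following initial evaluation by attending physician", and consent is taken. On blinding, it says "Fellow will be unblinded, attending physician blinded"; the fellow prepares the syringe and the attending injects. Unacceptable pain leads to a further injection of the assigned agent, and continuing pain to one more. After that the patient moves to lidocaine with epinephrine, and may ask for that switch at any time.

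**The concern.** In a randomised comparison, the eligibility criteria should make every participant suitable for either allocation. The authors evidently judged that allergy to a study agent belongs among the written exclusions, but they applied this to one arm only. The omitted substance is not an incidental ingredient: on the Introduction's account it is what makes bacteriostatic saline an anesthetic at all, and the saline arm is the one under test.

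What is at stake is the safety of a patient already known to be allergic to one of the two agents. As written, whether that patient avoids exposure depends on someone noticing outside the stated criteria. The concern does not extend to the pain outcomes or their analysis.

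**Working it through.** The plan has no figure to reproduce here, so the check sets the written criteria against the two agents.

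**Step 1. Test patient against the criteria in Participants.** Take an adult with an eyelid lesion, no sedating medication, no allergy to lidocaine or epinephrine, and a known allergy to the preservative alcohol.

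| Criterion | Names the preservative alcohol? | Result for this patient |
|---|---|---|
| Inclusion 1 (adult age) | No | Met |
| Inclusion 2 (eyelid lesion) | No | Met |
| Exclusion 1 (other sedating medication) | No | Not triggered |
| Exclusion 2 (allergy) | No | Not triggered |

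None of the four criteria (0 of 4) names the alcohol. The patient is eligible as written.

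**Step 2. Exclusion 2 against the active substances of each arm** (Intervention, with the Introduction for the saline arm).

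| Arm | Active substances | Covered by exclusion 2 |
|---|---|---|
| Lidocaine with epinephrine | Lidocaine; epinephrine | 2 of 2 |
| Bacteriostatic saline | Preservative alcohol | 0 of 1 |

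Counting the alcohol as the single active substance of the saline arm is a reading of the Introduction, which names no other.

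**Step 3. Steps before and at injection that might close the gap** (Study Protocol).

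- Patient-list review before the clinic day, and the attending's initial evaluation: either could bring an allergy to light, but no allergy check is specified.
- Consent: the consent pages were not available, so a warning there cannot be ruled out. A warning would still not be an eligibility criterion.
- Preparation of the drug: the fellow knows the allocation but is given no duty to compare it with the patient's history.
- Injection: the attending is blinded and so cannot match the agent to the patient at that moment.

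**Step 4. Opportunity for repeat exposure.** A lesion allocated to saline receives 1 initial injection plus 0, 1 or 2 pain-triggered repeats, so 1 + 0 = 1, 1 + 1 = 2 or 1 + 2 = 3 saline injections. A request for standard of care stops the sequence at whatever number has been reached. Because lesions are randomised separately, a patient with several lesions could receive saline at more than one site. These counts describe dosing under the protocol. They do not measure allergic risk.

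**The case against.** The strongest reply is that eligible on paper does not mean exposed. The allergy must already be known, and it would have to be missed by the attending at initial evaluation, by the patient at consent, and by the fellow drawing up a named drug. Blinding is no obstacle at the evaluation, because nothing has yet been allocated and the attending can consider both agents. The documents do not show that allergy histories go untaken. They also say nothing about how common or serious this allergy is, so they do not support calling it more than a small gap.

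There is also a partial reason for the asymmetry. Lidocaine with epinephrine is the fallback for anyone with continuing pain or who asks for it, so any participant in either arm may receive it. Allergy to those two substances therefore has to be excluded across the whole trial, which makes the contrast of 2 of 2 against 0 of 1 less telling than it first looks.

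Much of this stands as a limit on weight. Ordinary clinical care would probably catch most such patients, and the unseen consent pages might help. None of it closes the gap in the criteria. The fallback role explains why the lidocaine and epinephrine exclusion is needed, but not why the other agent's active substance is left out, since any enrolled lesion may be allocated to saline. If informal vigilance were enough, a written exclusion would be hard to justify for the control arm's substances too.

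**Conclusion.** The concern holds. The written criteria admit a patient with a known allergy to the active substance of the saline arm, and no other text available for review prevents that patient from being randomised to it. Confidence is high for the gap in wording. No claim is made about how often harm would follow.

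The conclusion rests on the Introduction's account of the alcohol as the anesthetic component of bacteriostatic saline, and on the general principle that no one should be randomised to an agent to which they are known to be allergic. The number affected cannot be estimated from the documents and is assumed to be small. The pain endpoints and the Statistical Plan are unaffected. The change should be made because it protects participants at almost no cost.

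**What to change.** Reword exclusion 2 to cover allergy or hypersensitivity to any component of either study agent, expressly including the preservative alcohol in bacteriostatic saline. Use the name on the product label: the Introduction writes benzoyl alcohol, while titles in the References write benzyl alcohol. State in Study Protocol that this is checked before the first lesion is randomised. The investigators should settle the clinical wording.

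The cost is one line in the eligibility list and one screening question. Probably very few patients would be excluded, although the documents give no frequency. No endpoint or analysis changes.

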#### Intervention

- 1. 0.9% Bacteriostatic Saline
- 2. 2% Lidocaine + 1/100,000 Epinephrine

#### **Outcome Measures**

Primary

- 1. Pain during injection (1-10)
- 2. Pain during procedure (1-10)

Secondary

- 1. Bleeding requiring >5 minutes of firm pressure or cautery
- 2. Need for additional anesthesia

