# **Statistical Plan**

Pain of injection and pain of procedure are recorded on a categorical scale and compared using Student T-Tests. Percent of lesions requiring reinjection and percentage of lesions with "severe" bleeding were compared using Chi-square tests. To see if lesions size had any effect on these metrics, the lesions will be divided into < 1 mm, 1-5 mm, and > 5 mm, and analysis will be repeated on these groups.

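### The bleeding outcome that is declared is not the one that is graded and tested, and the recorded grade cannot recover it

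*Combined protocol and SAP*

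**What the plan says.** Three sections of the combined protocol and SAP deal with bleeding.

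- **Outcome Measures** lists the first secondary outcome as "Bleeding requiring >5 minutes of firm pressure or cautery".
- **Study Protocol** says what is recorded: "Bleeding level (Mild, moderate, or severe) will be noted". For the lowest level the text reads "Mild is defined as not needing pressure to stop". For the middle level it reads "Moderate is defined as needing five minutes or pressure to stop", and for the top level it reads "Severe is defined as needing cautery or a pressure patch". No pressure duration is listed as a data item, and neither cautery nor a patch is listed separately.
- **Statistical Plan** gives the analysis: "percentage of lesions with 'severe' bleeding were compared using Chi-square tests". It then repeats the analyses within lesion-size groups.

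No section links the grade to the declared outcome.

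**The concern.** The declared event and the tested event have only cautery in common. Prolonged pressure counts only in the declared event, and a pressure patch counts only in the tested one. If the plan is followed as written, the trial will report a result for an event other than its declared secondary outcome, and the size-group analyses will carry the same mismatch.

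The comparison is one that readers will look for. Under Intervention, one arm contains epinephrine and the other does not, and bleeding is one of only two secondary outcomes. If the two definitions pick out different lesions at different rates in the two arms, the reported difference could be larger or smaller than the difference in the declared outcome.

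**Working it through.** The plan states no bleeding rate, sample size or power, so there is no figure of its own to reproduce. The check has two parts.

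**1. Classify each type of lesion under both definitions.** The wording for moderate can be read literally (any pressure) or as a slip in which *or* stands for *of* (pressure up to five minutes). Both readings are shown.

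| Lesion | Declared event | Grade, literal reading | Grade, slip reading | Tested event |
|---|---|---|---|---|
| No pressure, cautery or patch | No | Mild | Mild | No |
| Pressure up to 5 min only | No | Moderate | Moderate | No |
| Pressure over 5 min only | **Yes** | Moderate | None fits | **No** |
| Cautery | Yes | Severe | Severe | Yes |
| Patch, pressure over 5 min, no cautery | Yes | Severe | Severe | Yes |
| Patch, pressure up to 5 min, no cautery | **No** | Severe | Severe | **Yes** |

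Two rows disagree, and the reading of moderate does not remove either of them.

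No combination of grades recovers the declared event. Severe alone mixes cautery with patch and misses prolonged pressure. Moderate plus severe adds lesions that stopped within five minutes.

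**2. Effect on the risk difference.** For each arm, let

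- C = rate of pressure over 5 minutes only;
- D = rate of patch with pressure up to 5 minutes and no cautery;
- E = rate of lesions that are events under both definitions.

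Then declared rate = C + E and tested rate = D + E. Subtracting the arms (saline minus lidocaine with epinephrine), E cancels:

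tested difference − declared difference = (D_saline − D_lido) − (C_saline − C_lido).

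Lesions classified differently, per 100 in an arm = C + D.

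Every rate below is an assumption, shown as saline v lidocaine.

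| Scenario | C | D | E | Declared | Tested | Shift in difference |
|---|---|---|---|---|---|---|
| 1 | 8% v 3% | 2% v 2% | 5% v 2% | 13% v 5% (8 points) | 7% v 4% (3 points) | (2−2) − (8−3) = −5 |
| 2 | 2% v 2% | 8% v 3% | 5% v 2% | 7% v 4% (3 points) | 13% v 5% (8 points) | (8−3) − (2−2) = +5 |
| 3 | 1% v 0.5% | 1% v 0.5% | 5% v 2% | 6% v 2.5% (3.5 points) | 6% v 2.5% (3.5 points) | 0.5 − 0.5 = 0 |
| 4 | 10% v 0% | 0% v 0% | 5% v 5% | 15% v 5% (10 points) | 5% v 5% (0 points) | (0−0) − (10−0) = −10 |

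The lesions classified differently per 100 (saline and lidocaine) are 8+2 = 10 and 3+2 = 5 in scenario 1; 2+8 = 10 and 2+3 = 5 in scenario 2; 1+1 = 2 and 0.5+0.5 = 1 in scenario 3; and 10 and 0 in scenario 4. In scenario 4 every patch follows more than five minutes of pressure, and prolonged pressure alone produces the mismatch.

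**The case against.** The strongest defence reads the grades as a ladder: no pressure, then five minutes of pressure, then anything beyond that. Severe would then be a loose restatement of the declared outcome. A patch is itself sustained pressure, so a patch with five minutes or less may be rare. On the slip reading, a lesion past five minutes has no grade. Whoever records it must choose one and might well choose severe, in which case the lesion would be counted after all.

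Part of this stands. The two events would nearly coincide if every lesion still bleeding after five minutes received cautery or a patch, and if a patch counted as more than five minutes of firm pressure. The documents state neither condition. If that is the intent, writing it down would itself be the reconciliation that is needed. A recorder who graded a prolonged-pressure lesion as severe would be departing from the stated definition, which requires cautery or a patch.

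It is also fair to say that the scenarios prove nothing about size, that this is one secondary outcome, and that the two primary pain outcomes are untouched. The study procedures and the Statistical Plan mix past and future tense, so some data may already exist. If so, pressure times may not be recoverable.

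**Conclusion.** The concern holds. The declared event, the recorded grade and the tested event do not agree, and the grade alone cannot rebuild the declared outcome. That conclusion rests on the wording and needs no assumption about rates.

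The effect on the between-arm difference is undetermined in both size and direction. The assumed scenarios give shifts of −10, −5, 0 and +5 points, and the effect could be negligible if few lesions fall in the two mismatched groups. The plan should be corrected, but the problem is confined to this secondary outcome and its size-group repeats.

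**What to change.** Reconcile Outcome Measures, Study Protocol and Statistical Plan to a single bleeding definition.

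- **Record for each lesion:** pressure time (none, up to 5 minutes, more than 5 minutes), cautery (yes/no) and pressure patch (yes/no).
- **Test** the declared endpoint built from those fields, with an exact test if counts are small. If the sponsor prefers a different event, amend Outcome Measures to declare it before any comparison by arm is made.
- **Clear up** the wording of the moderate level so that every lesion has exactly one grade. Reporting the three-level grade descriptively is optional.
- **If data have already been collected** without these fields, report the graded result under its own definition and say that the declared outcome was not measured.

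This concerns what is recorded and analysed. It takes no position on how bleeding should be managed. The cost is a few form fields and revised wording, with no added patients or procedures.

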# **Study Protocol**

Prior to clinic day, patient list will be reviewed to identify potentially eligible patients. On the procedure day, eligible patients will be approached for participation following initial evaluation by attending physician. If patient amenable, patient will be consented for study. Photograph will be taken of the lesion directly in electronic medical record, and lesion circled using annotate function. Each lesion will be randomized separately using iPhone-based randomization application to either bacteriostatic saline or lidocaine with epinephrine. Fellow will be unblinded, attending physician blinded. Medication will be drawn up by fellow and handed to attending physician who will inject the medication. Immediately following injection, patient will be asked pain level on 0 to 10 scale, which was noted. Five minutes will be allowed to pass and then procedure will be commenced. If patient has more pain than acceptable to them, additional study agent will be injected and procedure re-started. If continued presence of pain, one more additional trial of the study agent will be allowed. If patient continues to have pain, medication will be defaulted to standard of care (lidocaine with epinephrine). Alternatively, if patient requests standard of care at any point, medication will be switched to this. Immediately following procedure, patient will be asked pain level on 0 to 10 scale, which was noted. Number of reinjections or need to default to standard of care will be noted. Bleeding level (Mild, moderate, or severe) will be noted. Mild is defined as not needing pressure to stop. Moderate is defined as needing five minutes or pressure to stop. Severe is defined as needing cautery or a pressure patch. Immediately following injection, patient will be asked pain level on 0 to 10 scale.

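### Patients may contribute several separately randomised lesions, but the analysis has no patient term: average type I error holds, while precision on both primary pain outcomes may be lost

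*Combined protocol and SAP*

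**What the plan says.** The Participants section admits adults undergoing minor eyelid procedures "in clinic with at least one lesion" and sets no upper limit. Under Study Protocol, the lesion is the unit of allocation: "Each lesion will be randomized separately using iPhone-based randomization application to either bacteriostatic saline or lidocaine with epinephrine". The section does not say whether the app allocates by simple randomisation or in blocks. The patient rates pain after the injection and again at the end: "Immediately following procedure, patient will be asked pain level on 0 to 10 scale". Several lesions in one patient therefore share a rater.

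The Statistical Plan says that the two pain scores are "compared using Student T-Tests". For the other outcomes it says "Percent of lesions requiring reinjection and percentage of lesions with 'severe' bleeding were compared using Chi-square tests". Lesions are then split into three size groups and the "analysis will be repeated on these groups". No section mentions pairing, a patient effect, a clustering adjustment, or a limit of one lesion per patient.

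**The concern.** Pain scores from one person tend to agree, because that person brings the same pain threshold and the same use of the scale to each lesion. An analysis that treats lesions as unrelated has two consequences when some patients have more than one.

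1. A patient with one lesion in each arm supplies a within-patient contrast free of between-patient variation. The unpaired t-test gives that contrast no extra weight, so both primary outcomes may be tested with less power than the same data allow.
2. The t-test standard error assumes independent lesions. Given the allocation that actually occurred, it is too small if few patients have lesions in both arms and too large if many do.

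**Working it through.** **Inputs.** The documents state no sample size, significance level, power, SD, lesion counts or correlation, so there is no planned figure to reproduce. All inputs here are assumptions: 60 lesions, independent 1:1 allocation of each lesion, two-sided 5% level, within-patient correlation ρ of 0.3, 0.5 or 0.7, and three layouts.

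- A: 40 patients with one lesion and 10 with two.
- B: 20 with one and 20 with two.
- C: 30 with two.

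The share w of lesions that come from two-lesion patients is 20/60, 40/60 and 60/60.

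**Step 1: precision with ρ known.** Relative to the simple difference, a lesion from a two-lesion patient carries information 1/(1−ρ²). The variance ratio, patient-aware over simple, is 1 / [w/(1−ρ²) + (1−w)]. At ρ = 0.5, 1/(1−ρ²) = 1.333:

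- A: 1/(0.333×1.333 + 0.667) = 1/1.111 = 0.90
- B: 1/(0.667×1.333 + 0.333) = 1/1.222 = 0.82
- C: 1/1.333 = 0.75

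**Step 2: precision with ρ estimated.** Simulation with a random-intercept model fitted by REML gives less favourable ratios, as expected. Power is for a 0.7 SD difference, planned t-test then patient-aware re-randomisation test.

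| Layout | Variance ratio, ρ = 0.3 / 0.5 / 0.7 | Power %, ρ = 0.3 | Power %, ρ = 0.5 | Power %, ρ = 0.7 |
|---|---|---|---|---|
| A | 1.00 / 0.95 / 0.82 | 75.0 → 74.1 | 75.1 → 76.4 | 75.8 → 82.1 |
| B | 0.98 / 0.86 / 0.64 | 75.3 → 75.5 | 76.3 → 81.4 | 76.2 → 90.3 |
| C | 0.94 / 0.77 / 0.53 | 74.1 → 76.3 | 75.9 → 84.6 | 76.2 → 95.0 |

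A repeat simulation at ρ = 0.5 gave variance ratios of 0.96, 0.85 and 0.78.

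**Step 3: average type I error.** Over independent lesion-level allocations with a common effect, the simulated t-test error was 4.6–5.3%. There is no inflation.

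**Step 4: error given the allocation drawn.** If a share d of two-lesion patients have one lesion per arm, true variance over t-test variance is v = 1 + wρ(1−2d), and the error is about 2[1 − Φ(1.96/√v)]. At ρ = 0.5:

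- A, 3 of 10 split: v = 1 + 0.333×0.5×0.4 = 1.067, error 5.8%. With 7 of 10 split: v = 0.933, error 4.2%.
- B, 6 of 20 split: v = 1 + 0.667×0.5×0.4 = 1.133, error 6.6%. With 14 of 20 split: v = 0.867, error 3.5%.
- C, 11 of 30 split: v = 1 + 0.5×(1 − 22/30) = 1.133, error 6.6%. With 18 of 30 split: v = 0.900, error 3.9%.

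Simulation over allocations at least this extreme gave t-test errors, few split / many split, of 6.2/4.1% (A), 6.7/2.7% (B) and 6.8/3.1% (C). The patient-aware test gave 4.7/5.2%, 5.0/4.5% and 5.2/4.7%. Few-split allocations are a minority. The binomial probability of at most 3 of 10, 6 of 20 or 11 of 30 is 17%, 6% and 10%.

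**Step 5: dependence on the app.** If the app uses blocks of 4, patients are split between arms more often than by coin toss and average t-test error falls to 4.7% (A), 4.0% (B) and 3.2% (C). The t-test is then conservative.

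**Step 6: effects that vary between patients.** With an effect SD of 0.7, t-test error is 5.7/5.8/6.3% in A/B/C and the patient-aware test gives 5.9/6.6/6.8%. Both run above 5% in every layout, and the fix does not cure this.

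**The case against.** A reader might infer that the plan counts correlated lesions as independent and so inflates type I error. That would follow if patients were randomised and all of a patient's lesions went to one arm. The protocol randomises each lesion separately, and step 3 shows average error near 5%. The inflation reading is not supported.

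A reader might equally infer that this trial will lose substantial power. The documents do not support that either. Nothing in them says how many patients will have several lesions, and layouts B and C are illustrations. In layout A the change is a slight loss at correlation 0.3 and about one point of power gained at 0.5.

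The strongest defence is that the planned t-test is valid over the randomisation described, so only efficiency and fit to the realised allocation are in question. That stands and limits the severity. It is also fair that the few-split errors are tail cases, and that the patient-aware estimate is more exposed to influence between lesions. If the agent used on one lesion shifts the score of the patient's other lesion by g, that estimate moves by about −0.19g, −0.37g and −0.51g in A, B and C at correlation 0.5. The simple difference moves by at most 0.03g.

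Nor is there a case for replacing the chi-square tests or dropping the size-group tests. A patient-aware version for binary outcomes showed no gain in layout A at a 20% event rate (few/many split 6.4/3.8%, against 6.0/4.3% for chi-square), and the problem described does not require removing the size groups.

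What survives is that the protocol openly permits several lesions per patient, and a standard analysis that uses this costs little.

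**Conclusion.** The point holds as a cheap improvement, severity minor. The mechanism is certain for any positive within-patient correlation when some patients have several lesions; its size in this trial is unknown. At 60 lesions and correlation 0.5, the variance ratio runs from 0.95 (10 two-lesion patients) to 0.77 (30). At correlation 0.3 with 10 such patients there is no gain. The t-test's error reaches about 6–7% only in the 6–17% of allocations with few split patients, and it is conservative where many are split. These results assume simple randomisation and, apart from step 6, a common treatment effect.

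**What to change.** Amend the Statistical Plan as follows.

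1. Record a patient identifier on each lesion record, and record the app's allocation scheme (simple or blocked, with block size). The test in item 2 cannot be run without that scheme, so establish it now.
2. For each overall pain outcome, estimate the treatment difference with a linear mixed model: treatment fixed, patient random intercept. Name one p-value in advance, from re-randomising lesions under the app's scheme, with the estimate divided by its standard error as the statistic. The model's own standard error gave 5.2–6.8% average error in simulation, and re-randomising the undivided estimate left the misfit of step 4 in place. If fewer than 10 patients have several lesions, apply the re-randomisation test to the simple difference in means instead. That count does not change under re-randomisation, so the rule cannot bias the test. With only 5 two-lesion patients the mixed-model test has power 72.0/73.6/75.7% at correlation 0.3/0.5/0.7, against 74.6/75.4/75.2% for the t-test.
3. Keep the planned chi-square and lesion-size analyses, and label the size-group results exploratory.
4. Report lesions and patients per arm and the number of multi-lesion patients, split between arms or not. Show the simple difference in means beside the model estimate, so that any influence between lesions can be seen.

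Cost: some SAP wording, one extra data field and slightly more analysis work. There is little or no gain if few patients have several lesions, and more weight falls on within-patient contrasts, which are exposed to influence between lesions treated at the same visit.

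### Procedure pain is asked once, after any re-injection or switch to lidocaine, with no worst/average/current wording and no rule for rescued lesions, so a real difference can shrink in saline's favor

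*Combined protocol and SAP*

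**What the plan says.** The Outcome Measures section lists pain during the procedure as the second of two primary outcomes, and the need for extra anesthetic as a secondary outcome.

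The Study Protocol section sets out a rescue ladder that runs before the pain question is put:

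- First failure: "If patient has more pain than acceptable to them, additional study agent will be injected and procedure re-started".
- Second failure: "If continued presence of pain, one more additional trial of the study agent will be allowed".
- Third failure: the lesion goes over to lidocaine with epinephrine.
- Shortcut: "Alternatively, if patient requests standard of care at any point, medication will be switched to this".

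The rating follows: "Immediately following procedure, patient will be asked pain level on 0 to 10 scale, which was noted". The plan also records rescue: "Number of reinjections or need to default to standard of care will be noted". It does not record pain at the moment of rescue.

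The Statistical Plan says of the scores: "Pain of injection and pain of procedure are recorded on a categorical scale and compared using Student T-Tests". It does not mention lesions that were re-injected or switched, except that "Percent of lesions requiring reinjection" is compared by chi-square.

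**The concern.** The Clinical question section asks whether saline anesthetizes adequately compared with lidocaine plus epinephrine. Procedure pain is the primary outcome that bears on this. For a lesion where saline failed, the single score is taken after the failure has been treated, possibly with the comparator itself. The rescue is asymmetric: a saline lesion can end on lidocaine, but a lidocaine lesion cannot end on saline.

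The outcome's name sets the time window as the procedure. It does not settle whether the patient should report the worst moment, an average, or the pain felt when asked. If the answer leans toward the later, rescued part, the highest saline scores are replaced by lower ones. The more often saline fails relative to lidocaine, the more of the difference disappears. From the primary result alone, a small difference could mean that saline worked or that the rescue worked.

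Comparing whole strategies, rescue included, is legitimate, but the plan does not say that this is what it is doing.

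**Working it through.** **No figure to reproduce.** The documents state no sample size, SD, expected means or rescue rate. Everything below is an illustration under stated assumptions.

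**Assumptions**
- Scores are normal with SD 2, rounded and clipped to whole numbers 0 to 10.
- The underlying lidocaine mean is 2, and the saline mean is 3, 3.5 or 4.
- A lesion is rescued when its score is at least T, with T = 5 or 6.
- All attempts on one lesion, including a lidocaine attempt after a switch, have correlation ρ = 0, 0.5 or 0.8.
- Patients report only the pain of the last attempt (relaxed below).

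**Formula.** Given the lesion's own effect, let f be the probability of a score ≥ T, ok the sum of x·P(x) over scores below T, and μL the lidocaine mean. With two re-injections and then a switch, the recorded mean is

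ok·(1 + f + f²) + f³·μL,

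averaged over lesion effects. The reference is the first-injection difference. After rounding and clipping it is 0.89, 1.37 and 1.85 for saline means 3, 3.5 and 4.

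**Worked example: saline mean 3.5, T = 5, ρ = 0**
- Saline: ok = 1.732, f = 0.3085. 1.732 × (1 + 0.3085 + 0.0952) + 0.0294 × 2.162 = 2.431 + 0.064 = 2.495.
- Lidocaine: ok = 1.577, f = 0.1056. 1.577 × (1 + 0.1056 + 0.0112) + 0.0012 × 2.162 = 1.762 + 0.003 = 1.764 (from unrounded values).
- Without rescue: 3.530 − 2.162 = 1.37. Recorded: 2.495 − 1.764 = 0.73. Loss: 1 − 0.730/1.369 = 46.6%.
- At ρ = 0.5 and 0.8 the recorded difference is 0.88 and 0.96.

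**Loss on the full ladder (saline mean 3 / 3.5 / 4)**

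| ρ | T = 5 | T = 6 |
|---|---|---|
| 0 | 42.8 / 46.6 / 51.0% | 26.2 / 29.8 / 33.7% |
| 0.5 | 31.0 / 35.7 / 41.2% | 18.0 / 21.6 / 26.0% |
| 0.8 | 23.8 / 29.9 / 37.1% | 12.5 / 16.5 / 21.6% |

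First-rescue rates behind these figures are 11–40% on saline and 4–11% on lidocaine. The share of saline lesions reaching the default to lidocaine is 0.1–6.5%, 1.7–17% and 4–26% at ρ = 0, 0.5 and 0.8.

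**Variations (ranges at ρ = 0, 0.5, 0.8)**
- Half of failing lesions ask for lidocaine at each of the first two failures: loss 30–58%, 21–48%, 15–43%.
- Pre-rescue pain gets half the weight in the answer: the loss halves, to 13–26%, 9–21%, 6–19%. In the example at ρ = 0 the recorded difference is (1.37 + 0.73)/2 = 1.05.
- Patients report worst pain: on the ladder the difference is 0.4% to 8.9% larger than the first-injection difference. If every failing lesion goes straight to lidocaine, it changes by −0.9% to +0.4%.

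**Simpler cross-check.** Assume SD 2, a true difference of 1.0, rescue in the saline arm only, and rescued lesions a random subset scored at the lidocaine mean. The observed difference is then 1.0 × (1 − r). At r = 30% it is 0.7, and with 63 lesions per arm power falls from 80% to about 50%.

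**The case against.** The strongest reply has four parts.

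1. **The loss depends on how patients answer.** Someone asked about the procedure they have just had may well include the painful stretch that led to re-injection. The largest losses need the reading furthest from the outcome's name. This stands: the plan does not show which reading applies, so shrinkage is possible, not established. That ambiguity is itself the defect.

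2. **Much of the loss is not contamination by lidocaine.** A second or third saline injection is still the assigned agent. With the same example (saline mean 3.5, T = 5), if a third failure keeps its own score and nobody is switched, the loss is 39.1, 20.0 and 8.4% at ρ = 0, 0.5 and 0.8, against 46.6, 35.7 and 29.9% with the switch. Repeat dosing therefore accounts for most of the loss at ρ = 0 and just over half at 0.5; the switch dominates at 0.8. Whether repeat dosing counts as bias depends on the question being asked, which the plan leaves unstated.

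3. **More rescue means more needle sticks.** If patients fold that discomfort into their answer, saline scores rise. This is a fair point, and the illustration omits it. It is another reason to define the question.

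4. **Failure is already reported.** Extra anesthetic is a secondary outcome and re-injection is tested, so unequal re-injection would be visible. This is a real safeguard, but it sits beside the primary score and does not change it. A default after continued pain has already been counted as a re-injection. A lesion switched on request without a re-injection has no stated place in that test.

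**Conclusion.** The concern holds. A primary outcome rests on one unqualified question asked after rescue that can include the comparator drug, with no earlier score and no rule for rescued lesions in the t-test. Shrinkage in saline's favor requires two things: more rescue on saline, and answers that lean toward post-rescue pain. Under the assumed means, SD and thresholds, the ladder loss runs from 12.5% to 51% at the extreme where only post-rescue pain is reported, and from 6% to 26% at half weight. It is essentially nil for worst pain. The true size in this trial is unknown. This should be fixed before data collection, because pre-rescue pain that was not asked for at the time cannot be recovered. It does not invalidate the trial.

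**What to change.** Leave the rescue rules as they are and change only measurement and analysis.

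1. For every lesion, word the end-of-procedure question as worst pain at any time during the procedure, including before any additional injection. Exclude the pain of the injections themselves, since injection pain is the other primary outcome. Make this the primary procedure-pain score, and state in the Statistical Plan that every lesion is analyzed in its randomized arm, rescue included.
2. Whenever more agent or a switch is given after the procedure has started, record a 0–10 score just before it.
3. Pre-specify a supportive analysis that uses the first pre-rescue score for rescued lesions and the end-of-procedure score for the rest. Lesions switched before any procedure pain keep their end-of-procedure score and are counted separately.
4. Report re-injection and switch to lidocaine (by default or on request) as two separate rates by arm, beside the primary result.

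The cost is one reworded question, one extra question per rescue and a few sentences in the Statistical Plan. There are three downsides. Worst-pain recall may raise scores slightly in both arms. A worst score is a maximum over more attempts in the arm rescued more often, so it can widen the difference a little (up to 8.9% in the illustration). The supportive analysis mixes in-the-moment and recalled scores, which is why it is not the primary. If lesions have already been enrolled, the analysis statement and the two separate rates can still be added.
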